Appendix 9: Summary of Versions and Changes79

Appendix 10: Sponsor Electronic Signature.....91

1. Synopsis

Protocol Title: A Phase 2b, Multicentre, Multinational, Double-blind, Dose-finding Study, incorporating an open label substudy, in Adult Patients with Type I, III or IV Osteogenesis Imperfecta Treated with setrusumab (BPS804)

Rationale:

There is limited clinical experience with setrusumab (BPS804) in the Osteogenesis Imperfecta (OI) patient population. MBPS205 will be the first study to investigate dose-response to setrusumab in a large cohort of Type I, III and IV OI patients.

Objectives and Endpoints

Objectives	Endpoints
Primary	

 To demonstrate that setrusumab increases radial trabecular volumetric bone mineral density (Tr. vBMD) on high resolution peripheral quantitative computed tomography (HRpQCT) and bone strength on finite element analysis (FEA) in patients with OI Type I, III or IV 	
 Tr. vBMD (radius) on HRpQCT and bone strength on FEA at 12 months.
Secondary	

 To determine the dose-response relationship of Tr. vBMD to setrusumab after 12 months of treatment 	
 Tr. vBMD (radius) on HRpQCT at 12 months.

 To evaluate the onset of treatment effect 	
 Tr. vBMD (tibia & radius) on HRpQCT and bone strength on FEA at 6 months. Tr. vBMD (tibia & radius) on HRpQCT and bone strength on FEA at 3, 6 & 12 months in the open-label treatment arm.

 To evaluate the effect of setrusumab on fracture rate (peripheral, major [long-bone], and vertebral fractures) 	
 Total fracture rate at 12 months Peripheral fracture rate at 12 months Vertebral fracture rate at 12 months Long-bone fracture rate at 12 months

Objectives	Endpoints

 To evaluate the effect of setrusumab on vertebral fractures and vertebral height 	
 Changes in vertebral fractures and vertebral height with Genant's semi-quantitative method and 6-point quantitative morphometry from baseline at 6 and 12 months

 To evaluate the effect of setrusumab on bone mineral density (BMD) 	
 Changes in lumbar, whole body, and proximal femur dual-energy x-ray absorptiometry (DXA) BMD (absolute and T-score) from baseline at Month 6 and Month 12.

 To evaluate the effect of setrusumab on bone quality 	
 Changes in bone histomorphometry

 To evaluate changes in radial Tr. vBMD on HRpQCT and bone strength FEA during the 12 months post-setrusumab treatment period 	
 Tr. vBMD (tibia & radius) on HRpQCT and bone strength on FEA at 18 and 24 months

 To evaluate the effect of setrusumab on HRpQCT parameters 	
 Changes (tibial and radial) in Total vBMD, cortical vBMD, bone volume fraction (BV/TV), peripheral to medullary trabecular bone density ratio (Met/Inn), trabecular thickness (TbTh), trabecular number (TbN), Inhomogeneity, cortical thickness, and cortical porosity from baseline at 6, 12, 18, and 24 months Changes in Tr. vBMD (tibia) from baseline at 12, 18, and 24 months Changes (tibial and radial) in Total vBMD, cortical vBMD, bone volume fraction (BV/TV), peripheral to medullary trabecular bone density ratio (Met/Inn), trabecular thickness (TbTh), trabecular number (TbN), Inhomogeneity, cortical thickness, and cortical porosity on HRpQCT and bone strength on FEA at 3 months in the open-label treatment arm.

 To evaluate the effect of setrusumab on body composition 	
 Changes in body height, weight and body mass index from baseline at 6 and 12 months Changes in lean and fat body mass from whole body DXA

Objectives	Endpoints

 To evaluate the effect of setrusumab on markers of bone composition 	
 Changes in bone turnover markers and metabolic biomarkers associated with bone (parathyroid hormone [PTH], amino-terminal propeptide of type 1 procollagen [P1NP], carboxy-terminal propeptide of type 1 procollagen [P1CP], osteocalcin [OC], bone-specific alkaline phosphatase [BSAP], carboxy-terminal telo-peptide [CTX-1], amino-terminal telo-peptide [NTX-1], receptor activator of nuclear factor kappa-B ligand [RANKL], osteoprotegerin, transforming growth factor beta [TGF-β], sclerostin, released C-terminal pro-peptide of Type V collagen [Pro-C5], neo-epitope of MMP-2,9 mediated degradation of Type V collagen [C5M]) from baseline and each visit

 To evaluate the effect of setrusumab on Patient-Reported Outcomes (PROs) and Quality of Life (QoL) 	
 Change in total scores from baseline to Month 6 and 12 on Short Form 12 Health Survey (SF-12), EuroQol 5-dimension 5-level descriptive system (EQ-5D-5L) and Osteogenesis Imperfecta specific Quality of Life Questionnaire for Adults (OIQoL-A) Change in OIQoL-A pain and activity sub-scale scores from baseline to Month 6 and 12

 To evaluate the pharmacokinetics (PK) of setrusumab 	
 Serum concentrations of setrusumab

 To evaluate potential induction of anti-drug antibodies (ADAs) by setrusumab and their effect on safety and PK 	
 Serum concentrations of anti-setrusumab antibodies Serum concentrations of setrusumab neutralising antibodies

 To evaluate safety and tolerability of setrusumab 	
 Treatment-emergent adverse events (TEAEs), treatment-emergent serious adverse events (TESAEs) Infusion site reactions Vital signs Physical examinations

[figure not shown]
Objectives	Endpoints
	
 • Electrocardiogram • Clinical laboratory tests
Tertiary/Exploratory	

 • To evaluate the effect of setrusumab on bone quality 	
 • Changes in Trabecular Bone Score from baseline at 6 and 12 months

 • To evaluate the effect of setrusumab on changes in use of physical aids 	
 • Changes in usage or need for physical aids from baseline at 12 months

 • To evaluate the effect of setrusumab on hearing 	
 • Change in auditory function from baseline at 12 months in a subset of patients

 • To evaluate the effect of setrusumab on bone formation and resorption parameters measured by HRpQCT 	
 • Change in bone formation from baseline at 6 and 12 months 
 • Normalised newly mineralised bone volume (MV/BV) • Normalised newly mineralised surface area (MS/BS) • Mineralised thickness (MTh) • Normalised formation patch number density (N.F. Patch/BV) • Formation patch volume (F.PatchVol.) • 3D bone formation rate (3D BFR/BS) • 3D mineral apposition rate (3D MAR) • Change in bone resorption from baseline at 6 and 12 months 
 • Normalised newly eroded bone volume (EV/BV) • Normalised newly eroded surface area (ES/BS) • Erosion depth (ED) • Normalised resorption cavity number density (N.R.Cav./BV) • Resorption cavity volume (R.Cav.Vol.) • 3D bone resorption rate (3D BRR/BS)

Objectives	Endpoints
	
 • 3D mineral resorption rates (3D MRR)

Overall Design:

- MBPS205 is a phase 2b, multicentre, multinational, double-blind, dose-finding study with 3 blinded doses of setrusumab (20 mg/kg, 8 mg/kg and 2 mg/kg) and an open-label treatment arm (20 mg/kg) in patients diagnosed with Type I, III or IV OI.
- Participants will be adults clinically diagnosed with either Type I, III or IV OI and a confirmed COL1A1/COL1A2 mutation who have fractured in the previous 5 years.
- Participants will be excluded if they are over 75 years old, have a history of certain cardiac events, have confounding skeletal or other medical conditions and/or have been treated with bisphosphonates in the previous 3 months or other anabolic or anti-reabsorptive medications in the previous 6 months.
- Participants will have HRpQCT scans of their non-dominant distal radius at baseline, 3-month (for open-label participants only), 6-month and 12-month time points to determine the effect of treatment on Tr. vBMD with the primary analysis and dose determination being made after all enrolled patients have completed their 12-month HRpQCT scan.
- Other investigations include study of sparse PK, monitoring for safety and tolerability including immunogenicity, and measurement of the effect of treatment on bone quality, fractures, QoL and utilisation of resources e.g. physical aids and hospitalisation.
- Following completion of the study treatment participants will enter 12 months follow-up and will have visits at Months 14, 18 and 24. Participants will also receive follow-up telephone calls at Months 16 and 21.
- During the follow-up period all participants will have the option to receive zoledronic acid at Month 12 and Month 18 at the discretion of their treating physician.
- During the follow-up period participants will have HRpQCT scans of their non-dominant distal radius and tibia at Month 18 and Month 24.
- For the purposes of the study protocol 1 month is defined as 28 days.
- An Independent Data Monitoring Committee will monitor safety throughout the study and make recommendations on the selected dose.

MBPS205 Study Schematic

Number of Participants:

The number of participants is based on power considerations for the trabecular vBMD (radius) derived from HRpQCT at Month 12. The primary analysis method for this endpoint will be on the change from baseline within each treatment group, so the primary hypothesis to be tested is

$$H_0: \mu_T \leq 0 \text{ vs. } H_1: \mu_T > 0$$

where μ_T denotes the change from baseline for each dose of Setrusumab. Under the assumptions of a maximum change from baseline of [REDACTED], a standard deviation at both timepoints of [REDACTED] and a correlation between both measurements of [REDACTED], a sample size of 25 patients per group yields approximately 80% power for a one-sided test with significance level 0.025, if the data are analysed on the log scale using a t-test.

For a change from baseline of [REDACTED], with standard deviation as above the one-sided test would have a probability of 80% to yield a p-value below 5%, being considered indicative of a trend.

Following a review of the trabecular vBMD (radius) derived from HRpQCT at Month 6 of those subjects within the 20 mg/kg Setrusumab open label treatment group, a change from baseline standard deviation of [REDACTED]³ was observed. This yields to a correlation between baseline and Month 6 visits of [REDACTED] (much higher than the [REDACTED] that was originally assumed). If such a correlation is observed at Month 12, given 25 subjects per arm, the one-sided test would have a probability of 80% to yield a p-value below 5% for a change in baseline of [REDACTED].

As a secondary analysis, the MCPMod approach will be applied to the data in order to assess a non-flat dose-response curve and to obtain information about the underlying dose-response curve. Due to the missing placebo group, the power of this approach depends heavily on the underlying dose-response curve.

The following candidate models will be used:

- EMax (ED₅₀ of 1.5 mg)
- Exponential ($\delta = 2$)

Under the assumptions of each of the two candidate models being the true dose-response curve, and in addition an Sigmoid EMax model with parameters ED₅₀ = 10 mg and h = 2.4, a contrast test at a one-sided significance level of 2.5% has the following power for each of the three models:

Model	EMax	Exponential	Sigmoid EMax
Power	13.7%	73.2%	60.7%

The total sample size required is therefore determined as 100:

- 25 participants on open-label setrusumab (20 mg/kg)
- 25 participants on each of the active arms (2 mg/kg, 8 mg/kg, 20 mg/kg)

Approximately 100 participants will be randomised.

Treatment Groups and Duration:

- Participants will be qualified during a 28-day screening period, followed by 12 months of study treatment. At the end of treatment in MBPS205, participants will continue into the follow-up period for 12 months. Participants discontinuing setrusumab treatment prior to the end of the treatment phase for any reason will complete the end of treatment visit and the 60-day follow-up visit.
- After screening, participants will be randomised to 1:1:1:1 to blinded 20 mg/kg, 8 mg/kg and 2 mg/kg setrusumab or to open label 20 mg/kg setrusumab.
- Any participants assigned to placebo according to the previous MBPS205 protocol design will be transferred to open-label 20 mg/kg treatment for 12 months.
- Allocation of treatment will be via Interactive Web Response System (IWRS), which will also calculate total doses of setrusumab based on participant body weight and track vials allocation to patients.
- Investigators and participants will be blinded to the blinded active arms study treatment allocation throughout the study; pharmacists will be unblinded to study allocation to allow for dispensing and reconstitution. The sponsor will be initially blinded but become unblinded after the primary analysis at which time all the participants will have been enrolled.
- All participants will receive monthly 60-minute infusions of 250 mL 5% dextrose with setrusumab.

Statistical Methods:

General Statistical Methods

The evaluation of the primary efficacy endpoint will be performed on the full analysis set (FAS, intention to treat analysis). Results for the per-protocol analysis set will be considered supportive. Safety endpoints will be analysed on the safety analysis set. The primary analysis will be performed after all patients have completed their initial 12-month study period or have withdrawn prior to completion. Analyses for the follow-up period will be carried out separately to the primary analysis once all patients have completed the 12 months follow-up period, or have withdrawn from it.

Generally, data will be tabulated by treatment group. Both descriptive and inferential statistics will be presented as appropriate. Categorical data will be described using absolute and relative frequencies; for continuous variables, the following descriptive summary statistics will be presented: number of observations, arithmetic mean, standard deviation, minimum, lower quartile, median, upper quartile, maximum. Continuous variables will be log transformed where appropriate. Time to event variables (e.g., time to first fracture) will be analysed using Kaplan-Meier methods, and quartiles for the median time to event will be presented together with their 95% confidence intervals.

Data for placebo participants and open-label BPS804 20 mg/kg participants will be reported separately from the comparison between the randomized, blinded treatment groups. In particular for the primary analysis, the open-label BPS804 20 mg/kg participants' data will not be pooled with the blinded BPS804 20 mg/kg participants' data.

Efficacy Analysis

The HRpQCT results will be log transformed and an ANCOVA model will be used to calculate Least Square Means (LSMeans) for the change from baseline, using baseline values as a covariate and treatment group and stratum as a factor. LSMeans for each treatment group will be calculated and tested against the null hypothesis of 0 in an a priori hierarchical approach, starting with the highest dose. Differences between LSMeans will also be displayed but will be analysed in an exploratory fashion only. The type I error rate will be 5% two-sided. P-values above 5% but below 10% (two-sided) will be considered as indicative for a trend.

The LSMeans will further be analysed using the MCPMod methodology, using the following candidate models:

- EMax (ED₅₀ of 1.5 mg)
- Exponential ($\delta = 2$)
- Sigmoid EMax model with parameters ED50 = 10 mg and h = 2.4

Parameter estimates and predicted values for each dose will be calculated for all models. These analyses will be done primarily on the trabecular vBMD (radius). It will be repeated for the bone strength on FEA for supportive evidence.

LSMeans and LSMean differences between treatment groups will be back-transformed to their original scale for descriptive purposes. After subtracting the geometric mean of the log baseline values, the back-transformed LSMeans will correspond to the percentage change from baseline,

while the back-transformed LSMeans differences will correspond to the ratio of percentage changes from baseline.

The remaining efficacy variables will be analysed according to their scale using general methods as described above.

Exploratory Analyses

Exploratory endpoint variables will be analysed according to their scale using general methods as described above.

Safety Analyses

Variables will be analysed according to their scale using general methods as described above, and results will be presented overall and by treatment group.

Follow-Up Period Analyses

Variables will be analysed according to their scale using general methods as described above. Results will be presented overall and by initial treatment assignment. In addition, subgroup analyses will be performed for HRpQCT, DXA, vertebral radiograph, CTX-1 and P1NP based on the administration of zoledronic acid during the follow-up phase (none; at Month 12; at Month 18). Also, the frequency of administration of zoledronic acid during the follow-up phase will be related both to the site and to the 12 months outcome for both primary efficacy endpoints.

HRpQCT Validation Analysis

Validation analyses to the HRpQCT measurements will be described in a separate analysis plan.

2. Schedule of Activities (SoA) Treatment Period

Procedure	Screening (up to 28 days before Day 1)	Months													Notes All visits ± 4 days.	
		Base-line	1	2	3	4	5	6	7	8	9	10	11	EOT/12		
COL1A1/COL1A2 Mutation confirmation	X															If not available, consent can be obtained and test conducted prior to main study screening
Informed consent	X															Main study consent and bone biopsy
Inclusion and exclusion criteria	X															Re-confirm at Baseline
Demography	X															
Full physical examination including height and weight	X							X							X	
Brief physical examination		X	X	X	X	X	X		X	X	X	X	X			
Past and current medical conditions	X															
Prior medications	X															In the last 2 years

Procedure	Screening (up to 28 days before Day 1)	Months													Notes All visits ± 4 days.	
		Base-line	1	2	3	4	5	6	7	8	9	10	11	EOT/12		
Serum pregnancy test (WOCBP only)	X															
Urine pregnancy tests (WOCBP)		X	X	X	X	X	X	X	X	X	X	X	X	X	X	
Safety Laboratory assessments	X	X	X	X	X			X			X			X	To be collected pre-dose	
25-OH-Vitamin D	X	X	X		X			X			X			X		
12-lead ECG	X							X						X		
Vital signs	X	X	X	X	X	X	X	X	X	X	X	X	X	X		
Randomisation		X														
Study treatment		X	X	X	X	X	X	X	X	X	X	X	X		Weight will be measured to calculate dose	
HRpQCT	X				X			X						X	M6 and M12 scans be conducted ±7days of visit M3 for open-label participants only	
DXA	X							X						X	Calcium tablets should not be taken 2 hours prior to DXA lumbar scan	

Procedure	Screening (up to 28 days before Day 1)	Months													Notes All visits ± 4 days.	
		Base- line	1	2	3	4	5	6	7	8	9	10	11	EOT/ 12		
Vertebral Radiograph	X							X							X	
Fracture Assessment & Radiograph		←-----→													Radiographs will be taken in the event of a symptomatic fracture	
Bone Biomarkers		X	X		X			X				X			X	Fasting pre-dose blood draw, Sub-set of patients will have additional blood draws at 8 d post- baseline (+4 days) and 14 d post-M9 visit.
Bone Biopsy								X							X	Sub-set of participants. Completed once either at M6 or M12
Audiometry	X														X	This procedure can be omitted if the investigative site does not have the capability to complete the audiometry assessment
Patient-Reported Outcomes		X	X		X			X			X				X	

Procedure	Screening (up to 28 days before Day 1)	Months													Notes All visits ± 4 days.	
		Base-line	1	2	3	4	5	6	7	8	9	10	11	EOT/12		
Setrusumab PK		X	X	X	X			X							X	Sub-set of patients will have additional blood draws at 8 d post-baseline. Samples taken pre-dose and 10 mins post-dose at treatment visits. One sample taken at non-treatment visits
Anti-setrusumab Antibodies		X	X	X	X			X							X	Sub-set of patients will have additional blood draws at 8 d post baseline. Taken pre-dose for treatment visits
Zoledronic acid treatment															X	Optional. Can be administered up to 2 months following the visit
AE/SAE/AESI review		←-----→														
Concomitant medication & physical aid/treatment review		←-----→														

3. Schedule of Activities (SoA) Follow-Up Period

Procedure	Months					Notes All visits \pm 4 days.
	14 (Follow-up visit +60 days)	16	18	21	24	
Follow-up call		X		X		
Brief physical examination	X		X		X	
Urine pregnancy tests (WOCBP)	X					
Safety Laboratory assessments	X		X		X	
25-OH-Vitamin D	X		X		X	
12-lead ECG	X					
Vital signs	X		X		X	
HRpQCT			X		X	Scans be conducted \pm 7 days of visit
DXA			X		X	Calcium tablets should not be taken 2 hours prior to DXA lumbar scan
Vertebral Radiograph			X		X	
Fracture Assessment & Radiograph	←-----→					Radiographs will be taken in the event of a symptomatic fracture
Patient-Reported Outcomes			X		X	
Setrusumab PK	X					One sample taken at non-treatment visits

Procedure	Months					Notes All visits ± 4 days.
	14 (Follow-up visit +60 days)	16	18	21	24	
Anti-setrusumab Antibodies	X					
CTX-1 & P1NP	X		X			Tested locally. ± 2 months of visit
Zoledronic acid treatment			X			Optional. Can be administered ± 1 month from visit
AE/SAE/AESI review	←-----→					Reporting only SAEs only after Month 14
Concomitant medication & physical aid/treatment review	←-----→					

4. Introduction

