Appendix 2: Clinical Laboratory Tests

- The tests detailed in the table below will be performed by a central laboratory unless otherwise stated.
- Protocol-specific requirements for inclusion or exclusion of participants are detailed in [Section 7](#) of the protocol.
- Additional tests may be performed at any time during the study as determined necessary by the investigator or required by local regulations.

Protocol-Required Safety Laboratory Assessments

Laboratory Assessments	Parameters			
Haematology	Platelet Count	White Blood Cell count with Differential:		
	Red Blood Cell Count	Neutrophils		
	Haemoglobin	Lymphocytes		
	Haematocrit	Monocytes Eosinophils Basophils		
Clinical Chemistry ¹	Blood Urea Nitrogen	Potassium Chloride, Bicarbonate/Carbon dioxide	AST ALT Alkaline phosphatase	Total and direct bilirubin
	Creatinine	Sodium	Thyroid stimulating hormone	Total Protein
	Glucose (non-fasting)	Calcium Vitamin D	Lipase	Prothrombin Time/ international normalised ratio
Routine Urinalysis	
 • Specific gravity • pH, glucose, protein, blood, ketones by dipstick • Microscopic examination (if blood or protein is abnormal) • Albumin creatinine ratio and protein creatinine ratio to be tested at site (if albumin or protein is abnormal) 			
Other screening Tests	
 • Follicle-stimulating hormone and estradiol (as needed in women of non-childbearing potential only) • Serum or urine human chorionic gonadotropin pregnancy test (as needed for women of childbearing potential)² 			

	
 The estimated glomerular filtration rate (eGFR) will be calculated based on Cockcroft-Gault formula: $\text{eGFR} = ((140 - \text{Age}) / (\text{SerumCreat})) * (\text{Weight}/72)$ All study-required laboratory assessments will be performed by a central laboratory, with the exception of COL1A1/COL1A2 genotyping. The results of each test must be entered into the eCRF.

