8.1.5 Definition of Baseline

Unless otherwise stated, Baseline will be the last assessment value before first study dose of study medication. For patients that were randomised to placebo prior to protocol amendment 4.0, assessments taken while on placebo may be utilized for the baseline derivation of each parameter.

For HRpQCT scan parameters baseline assessments maybe collected up to 10 days post the first dose of study medication.

Change from Baseline is defined as (value at assessment date – baseline value).

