8.1.6 Visit dates

For each visit, the date recorded by the Investigator in the eCRF will be considered as the visit date in all the algorithms and the listings.

Outputs will include all data collected from screening through to the end of the follow-up period.

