8.5.3.7 Bone Turnover Markers and Metabolic Biomarkers

Changes in baseline in the below bone turnover markers and metabolic biomarkers (and their log transformed values) at each visit will be analysed using ANCOVA in the same manner as the change from baseline in Tr.vBMD (radius) on HRpQCT (see Section 8.5.2.1):

- Parathyroid hormone [PTH]
- Aminoterminal propeptide of type 1 procollagen [PINP]
- Carboxy-terminal propeptide of type 1 procollagen [PICP]
- Osteocalcin [OC]

- Bone-specific alkaline phosphatase [BSAP]
- Carboxy-terminal telo-peptide [CTX-1]
- Amino-terminal telo-peptide [NTX-1]
- Receptor activator of nuclear factor kappa-B ligand [RANKL]
- Osteoprotegerin
- Transforming growth factor beta [TGF- β]
- Sclerostin
- Released C-terminal pro-peptide of Type V collagen [Pro-C5]
- neo-epitope of MMP-2
- 9 mediated degradation of Type V collagen [C5M]

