8.5.4.5 Follow-up Period Subgroup Analysis

A subgroup analysis (descriptive statistics and associated ANCOVA analyses) will be performed for HRpQCT, DXA, vertebral radiograph, CTX-1, and P1NP parameters at all follow-up visits by the administration of zoledronic acid during the follow-up period (none; at Month 12; at Month 18).

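### Follow-up CTX-1 and P1NP are tested locally within ±2 months but analysed as change from an apparently central baseline, so assay and timing differences cannot be separated from change after treatment (minor)

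*Protocol*

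**What the plan says.** **Where and when.** In the follow-up schedule (Protocol section 3), CTX-1 and P1NP are due at Months 14 and 18, with the note "Tested locally. ± 2 months of visit". The general visit window there is ±4 days, and HRpQCT has ±7 days. Protocol 10.7 makes follow-up testing of these two markers permissive, names no laboratory, and refers to a laboratory manual.

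**Baseline assay.** Protocol Appendix 2 says: "All study-required laboratory assessments will be performed by a central laboratory, with the exception of COL1A1/COL1A2 genotyping". The treatment-period biomarker row carries no local-testing note. SAP 8.1.5 adds: "Unless otherwise stated, Baseline will be the last assessment value before first study dose of study medication".

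**Analysis.** SAP 8.5.3.7 states: "Changes in baseline in the below bone turnover markers and metabolic biomarkers (and their log transformed values) at each visit will be analysed using ANCOVA". It follows the method of SAP 8.5.2.1, in which each group's LSMean is tested against zero. SAP 8.5.1 gives the model terms: treatment, randomisation stratum and baseline value. SAP 8.5.4.5, in line with Protocol 11.3.4, adds descriptive statistics and the associated ANCOVA for "CTX-1, and P1NP parameters at all follow-up visits by the administration of zoledronic acid during the follow-up period", in three classes (none, Month 12, Month 18).

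**Visit assignment.** Under SAP 8.1.6, "the date recorded by the Investigator in the eCRF will be considered as the visit date in all the algorithms". Neither document gives an analysis window for these samples or a bridging rule between laboratories.

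**Zoledronic acid.** It is optional, at the physician's discretion (Protocol 8.1.1). The schedules allow the Month 12 infusion up to 2 months after that visit and the Month 18 infusion within 1 month either side.

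**The concern.** If baseline is central and follow-up local, each change score is a local reading minus a central one. Any difference between the two methods enters that score in full, and nothing in the model can remove it. A reader of the follow-up report could not tell a fall in P1NP after setrusumab from a laboratory that reads low.

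Timing adds a second problem. The ±2-month window is wide compared with the spacing of the visits and of the infusions. Samples sharing a visit label can come from quite different stages of offset, and samples in one zoledronic acid subgroup can come from before or after the infusion that defines it.

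At stake is the reading of the only two bone markers scheduled after treatment ends. The Month 12 conclusions are not at stake.

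**Working it through.** The documents give no power or error figure for these markers, so there is none to reproduce.

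**1. Timing.** Inputs: 1 month = 28 days (Protocol synopsis and 6.1); last scheduled infusion at Month 11 (Protocol section 2); sample and infusion windows as above. I read the ±2 months as applying to the blood draw. Days are nominal, counted from baseline.

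- Last dose: 11 × 28 = Day 308.
- Month 14 sample: 14 × 28 ± 56 = Day 336 to 448, which is 28 to 140 days after the last dose.
- Month 18 sample: 18 × 28 ± 56 = Day 448 to 560, which is 140 to 252 days after.
- The windows meet at Day 448, so a participant's two samples can be 0 to 224 days apart (nominal 112).
- Month 12 infusion: Day 336 to 392. Month 18 infusion: 17 × 28 to 19 × 28 = Day 476 to 532.

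| Sample | Relative to Month 12 infusion | Relative to Month 18 infusion |
|---|---|---|
| Month 14 | 336 − 392 = −56 to 448 − 336 = +112 days | always before |
| Month 18 | 448 − 392 = +56 to 560 − 336 = +224 days | 448 − 532 = −84 to 560 − 476 = +84 days |

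So at Month 14 the Month 12 subgroup can mix pre- and post-infusion samples. At Month 18 the Month 18 subgroup can do the same.

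**2. How an assay difference enters.** On the log scale, let a local laboratory read δ above the central one. Observed change = true change + δ. Baseline is measured without δ, so adjusting for it does not remove δ, and each group's LSMean moves by the mean δ in that group. This has three consequences.

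- *Within-group change* carries the whole mean shift.
- *Zoledronic acid contrast:* a shift common to all local laboratories cancels on the log scale. Differences between laboratories do not cancel if prescribing follows site.
- *Randomised dose contrasts:* randomisation is stratified by OI type, not site, so δ is balanced in expectation and adds variance. With residual SD 0.3 to 0.5 and a between-laboratory SD of 0.2, the SD becomes √(0.09 + 0.04) = 0.36 to √(0.25 + 0.04) = 0.54.

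**3. Illustrative size.** The log-change SD of 0.3 to 0.5, the mean shift and the between-laboratory SD are my assumptions; none is in the documents.

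For one arm with n = 25, no true change and a two-sided 5% t-test against zero, the noncentrality is ln(1 + shift) × √25 / SD. For a 10% shift and SD 0.3 it is 0.0953 × 5 / 0.3 = 1.59.

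| Shift | SD 0.3 | SD 0.4 | SD 0.5 |
|---|---|---|---|
| 10% | 33% | 21% | 15% |
| 20% | 83% | 59% | 42% |

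The entries are probabilities of a false finding of change. Because testing is optional, n may be below 25, which lowers them.

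For the zoledronic acid contrast I used a simulation of 4000 runs with 100 participants, 28 sites, one laboratory per site and no true effect:

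| Between-laboratory log SD | Prescribing all-or-none by site | Prescribing independent of site |
|---|---|---|
| 0 | 4.9–5.0% | 4.6–5.6% |
| 0.1 | 6.4–8.8% | 4.4–5.2% |
| 0.2 | 11.3–17.7% | 4.9–5.4% |
| 0.3 | 16.1–23.5% | 4.6–5.1% |

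The entries are type I error over SD 0.3 to 0.5. The first row shows that a common method restores the nominal rate. The all-or-none column is an extreme case.

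**The case against.** Several stronger readings are tempting, and the documents do not carry them.

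- *A reader might infer a flat contradiction with Appendix 2.* Its opening line allows for exceptions stated elsewhere, its table covers safety tests and lists neither marker, and it has other site-tested items. The schedule note may be such an exception. That weakens the contradiction, but local values would still be set against the earlier baseline.
- *A reader might take the central baseline as stated.* It is inferred. The laboratory manual, which is not available here, may name the laboratory or hold a bridging rule.
- *A reader might infer that assay differences will be reported as loss of drug effect or as a zoledronic acid effect.* The documents support only that they cannot be separated.
- *A reader might infer that site determines both laboratory and prescribing.* Nothing says the laboratory is fixed by site. Protocol 11.3.4 and SAP 8.4.6 examine zoledronic acid use by site without predicting that it varies. If use is unrelated to site, the contrast stays near 5%. Nor do few participants per site make matters worse: random laboratory differences average over many laboratories. A common shift does not average out, whatever the number per site.
- *A reader might infer that the SAP discards the draw date.* SAP 7.1.1 and 8.1.5 refer to assessment date, so it may be available. What is missing is a rule that uses it.

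The importance is also limited. Testing is optional, the subgroup analysis sits under exploratory endpoints (SAP 8.5.4), follow-up results go into a report addendum (SAP 8.7.4), and the endpoints listed for the post-treatment objective are Tr. vBMD and bone strength. All of this stands and sets the severity.

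**Conclusion.** The concern holds as a minor one. As written, the SAP would run change-from-baseline ANCOVA on locally assayed CTX-1 and P1NP against a baseline that appears to be central, with no term or rule for laboratory or draw time. Within-group change then cannot be separated from a local-versus-central difference, and the zoledronic acid comparison cannot be separated from differences between local laboratories where prescribing follows site. Neither the size nor the direction of the bias can be derived from the documents; the percentages above are illustrations.

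The timing result rests only on stated windows: a spread of 112 days within each visit label, and subgroups that can mix pre- and post-infusion samples. Randomised dose contrasts mainly lose precision. If the laboratory manual shows the same method throughout, or a bridging rule, the assay part falls away and the timing part remains.

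**What to change.** 1. **SAP 8.5.3.7 and 8.5.4.5.** Do not run change-from-baseline ANCOVA on locally assayed CTX-1 and P1NP unless baseline was measured by the same laboratory and method. Otherwise report the values descriptively, or as a within-participant log ratio of Month 18 to Month 14 from the same laboratory. That ratio cancels a constant proportional bias, so no site factor is needed. With all-or-none prescribing by site, a fixed site factor would also make the zoledronic acid effect inestimable.
2. **SAP 8.1.6, for these two markers.** Use the actual draw date and report days since the last setrusumab dose. In the subgroup analysis, classify each sample as before or after any zoledronic acid infusion; this applies to both samples in the ratio.
3. **Protocol.** Reconcile the follow-up schedule note with Appendix 2 on where these markers are assayed, and use the central method where samples can be shipped.

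**Cost.** Items 1 and 2 need SAP wording only, provided draw dates are recorded; Protocol 8.6 already requires medication dates. Locally assayed values lose their change-from-baseline analysis, and some subgroup cells become smaller. Central assay under item 3 costs more than an extra tube at the safety draw: Protocol 10.7 calls for a 10 mL fasting sample, whereas the safety glucose in Appendix 2 is non-fasting, and tying the draw to a ±4-day visit would remove the present flexibility.
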